A randomized controlled trial is planned for this aim because our understanding of the patient, family, and health systems covariates that might affect our outcomes is limited; randomization is essential to the study design in order to avoid potential bias of intervention effect. Randomization will allow us to balance unknown or unmeasured potential confounders. While it is impossible to blind patients to the trial arm, an earnest effort will be taken to blind the clinical research staff completing the 14-day follow-up call to the intervention assignment.

We will complete a single center, randomized, standard-of-care-controlled prospective study to determine the effectiveness of a nurse phone call program, an intervention adapted from those studied in other populations (i.e., adults, high-risk infants) and re-engineered through Aim 2, in improving pediatric patient transitions from hospital to home. We hypothesize that a structured nurse telephone call within 4 days of hospital discharge will significantly reduce the proportion of patients requiring unplanned health system utilization in the 30-day post discharge period compared to patients receiving standard-of-care. We also hypothesize that there will be a significant improvement in family-defined outcome measures that will be identified in Aim 1.

Control patients will be randomized to receive standard-of-care at discharge. This care at our institution includes pediatric hospitalist to PCP verbal and written communication prior to discharge, written documentation for the family regarding prescribed medication regimen, recommended follow-up with outpatient PCP and relevant consultant(s), and delivery of prescribed medications from the hospital pharmacy to the patient's bedside. Patients randomized to the intervention arm will receive the same standard-of-care plus a nurse phone call within days of discharge.

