Enrolled patients and their families will be randomized 1:1 after discharge to the intervention group or standard-of-care using a permuted block randomization stratified by home state of residence (Ohio vs. Kentucky) to ensure equal allocation of the intervention within each stratification block. Random permutations within each block within each stratum will be generated using a random number generator available in SAS Proc Plan. The use of randomization in the study design is crucial for avoiding bias in the evaluation of the effectiveness of the nurse phone call intervention. Patients and families cannot be blinded given that the nature of the intervention is a nurse phone call. However, we will attempt to mitigate the potential bias in the following manner: 1) Families will be asked to refrain from disclosing intervention status to the interviewer at the follow-up phone call; and 2) Study staff will be blinded to treatment assignment when making the follow-up phone call. Study staff will use a written script to administer the survey. At the start of the call, families will be reminded to refrain from disclosing their intervention status.

Post-Hoc Analysis

Qualitative Analysis: The post-hoc analysis of this proposal will use qualitative methods, specifically interviews and focus groups. At the completion of the post-hoc analysis, we will have an improved understanding of the experiences, challenges, and successes of pediatric inpatient-to-outpatient transitions from the perspective of families and providers. Qualitative methods are the best means to generate consensus themes about patient and family experiences and preferences during inpatient-to-outpatient transitions. Interviews will be used to gain insight into what families and providers believe to be both the most relevant barriers to successful transition and the outcomes they find to be most meaningful. Participants will respond to semi-structured interviews and focus groups. The interviewer will use follow-up probes to expand and clarify responses and further elucidate the context of the responses. This qualitative methods process will permit us to gain unique perspectives and understand more deeply our results.

Readmission Analysis:

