We have multiple planned analyses to examine potential heterogeneity of treatment effect of the nurse visit. Factors included in the HET analysis are insurance, primary care access, financial strain, caregiver education, hospital service, and medical complexity. Medical complexity will be determined by the pediatric medical complexity algorithm (PMCA). The PMCA is a publicly available algorithm that identifies children with complex chronic disease (who have accessed tertiary hospital care). The algorithm includes three levels of medical complexity: children with complex chronic disease (C-CD), children with non-complex chronic disease (NC-CD), and children without chronic disease (CD). In order to calculate the PMCA we will collect additional administrative data for all patients enrolled in Aims 3 and 4. This data will include: ICD9 Codes/ICD10 codes, procedure codes, admission date, discharge dates, admitting and discharge departments. We will capture all outpatient, urgent care, ED, and hospital events within the specified time window (February 1, 2012 to April 30, 2016). The PMCA will be calculated based on a 3-year window before the index hospitalization.

Aim 4

Analyses: For the primary outcome, the dependent variable will be a dichotomized indicator of any occurrence of healthcare reutilization within 30 days of hospital discharge. Differences between phone intervention and control groups on this outcome will be evaluated using logistic regression with census tract poverty and discharge service unit included in the model. Other potential covariates (e.g. baseline characteristics with large differences between groups) will be included in a secondary analysis model evaluating the effectiveness of the phone intervention. For secondary outcomes, PDCS total score and number of days back to normal routine perceived by the caregiver at 14-day post-discharge will be analyzed as continuous variables. Differences between the phone intervention and control groups will be evaluated using linear regression with census tract poverty and discharge service unit and other potential covariates included in the model.

Sample size: Assuming a 20% reutilization rate in the control group, a sample size of 750 in the control group and 450 in the phone intervention group will achieve 80% power to detect a 7.1% decrease in reutilization rate (12.9% event rate) for the phone call intervention group with alpha=0.05, allowing for 11% noncompliance.

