2.2.4 Per-Protocol Analysis (PPA) population

Patients in the ITT-A population who have no major protocol deviations/violations, as determined by the H2O study PIs, will be included in the PPA presentation and analyses. PPA will be defined by intervention adherence (received the nurse phone call within 96 hours for those in the home visit arm, did not receive a traditional home visit for those in the control arm within 96 hours), and completed (or partially completed) the 14 day follow-up survey within 14+9 days of index discharge date.

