2.3.1 Description of study population

Sample size:

The total number of patients who are screened, consented, randomized, and withdrawn will be given. A summary of patients with protocol violations, such as failed nurse phone call, or who were withdrawn will be provided.

Demographics and Clinical Characteristics, Patient and Parent:

Demographic and clinical characteristics as measured at baseline will be summarized by trial arm. Variables to be summarized are: child age, only child indicator, first hospitalization indicator, parent or caregiver age, race/ethnicity, education, marital status, household income, employment status, primary payor, financial strain, access to primary care, census track poverty (high vs. low percentage below poverty), state of residence (Ohio vs. Kentucky). Primary discharge diagnosis ICD9 or ICD10 codes will be categorized using the AHRQ CCS algorithm. Variables will be summarized using descriptive statistics appropriate for each type of data item.

Baseline characteristics with large differences between groups will be included in analyses evaluating the effectiveness of the intervention.

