
Appendix: Data Management Plan

Data sources:

- 1) Interview data entered into REDCap (Research Electronic Data Capture)
- 2) EHR data (EPIC is the EHR system used at CCHMC) labeled CSV files transmitted via SFTP
- 3) HealthBridge labeled CSV files transmitted via SFTP
- 4) Home Care Epic database
- 5) HNCC Care Management participation
- 6) Readmission risk stratification data (data coming from [name])
- Interview data at discharge and 14-days, including patient medical record number, will be
 entered into REDCap and stored on SQL secured servers hosted by CCHMC's Biomedical
 Informatics (BMI) division, with state of the art security features including audit trails and
 password protection.
- For patients enrolled in the supplement, select CCHMC EPIC data fields, including patient demographics, index admission characteristics, readmission, revisit data within 30-days of discharge, and nurse phone visit characteristics (for the intervention arm only), will be extracted from the EHR EPIC system by CCHMC BMI staff and sent to CCHMC Data Management Center (DMC).
- HealthBridge routinely receives inpatient and emergency department admission and discharge information from hospitals across the Greater Cincinnati-Dayton community. As of January 1, 2015, all the local hospital systems (except for VA) were part of HealthBridge, which includes the hospital based free standing emergency units/urgent care. Using a patient panel provided by CCHMC DMC of patients enrolled in the supplement, HealthBridge will match and track admission information for these patients. Healthbridge has an automatic patient match rate of 98.2%. Of the remaining 1.8%, 99.5% of those have suggested matches that are staff reviewed and linked. The remaining records are reviewed and manually matched by staff. A complete file will sent to CCHMC DMC every 6 months.
- The data sources will be linked together using CCHMC patient medical record number. The statistical software SAS will be used to import and merge data sources and to create analysis datasets. This will be done by CCHMC DMC.
- We will use guidelines set by Clinical Data Acquisition Standards Harmonization (CDASH) version
 1.1, whenever possible for data collection fields. This standard guideline includes recommended
 data collection fields for 18 domains; including demographics, adverse events and other
 common domains that are common to most therapeutic areas and phases of clinical research.

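### The SAP extracts nurse-call data for the intervention arm only and its control-arm per-protocol rule checks a different service, so calls to controls would go unreported

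*SAP*

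**What the plan says.** The call is the only planned difference between the Aim 4 arms. Protocol, Study Design, Aim 4: "Patients randomized to the intervention arm will receive the same standard-of-care plus a nurse phone call within days of discharge". SAP 2.3 analyses patients in their allocated groups whatever they received.

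Four places bear on whether receipt of the call is known in each arm:

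- **SAP Appendix, Data Management Plan.** The Epic extract sent to the data management center covers patients enrolled in the supplement, but for the call it takes "nurse phone visit characteristics (for the intervention arm only". The same appendix lists a "Home Care Epic database" as a separate source, without describing its contents or stating an arm limit.
- **SAP 2.2.4, per-protocol population.** Adherence in the intervention arm, which the text calls the home visit arm, means receiving the nurse call within 96 hours. For controls it means the child "did not receive a traditional home visit for those in the control arm within 96 hours".
- **SAP 2.3.1.** "A summary of patients with protocol violations, such as failed nurse phone call, or who were withdrawn will be provided". The one example is an event that can occur only in the phone arm.
- **Protocol, Study Design, Aim 4.** "Families will be asked to refrain from disclosing intervention status to the interviewer at the follow-up phone call". The 14-day interview is therefore not set up to learn who was called.

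No section says that receipt of the call by a control will be extracted, counted or reported.

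**The concern.** A trial whose arms differ by one contact should be able to show how far they differed in that contact. Here receipt is to be measured on one side and left unmeasured on the other. The arm limit is a written rule of the extract, so a data manager who follows the SAP will not look for calls to controls.

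Two outputs are affected. First, the report cannot give the achieved separation in call receipt beside the intention-to-treat result, so a reader cannot judge how much dilution, if any, that result carries. Second, the per-protocol set screens controls for the wrong service: a control who received the trial's intervention passes the check. A per-protocol analysis is meant to remove such children.

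Interpretation matters more than usual here, because the protocol (Purpose of Study) reports that the parent home-visit trial gave an unanticipated result, with higher odds of unscheduled revisits in the intervention arm.

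**Working it through.** **Step 1. Set the rules side by side for a control child who is called within 96 hours.**

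| Planned element | Would it identify the child? |
|---|---|
| Epic extract (SAP Appendix) | No, call data are taken for the other arm only |
| Control adherence rule (SAP 2.2.4) | No, it checks for a traditional home visit |
| Violation summary (SAP 2.3.1) | Not stated; the example is a failed call |
| 14-day interview (Protocol, Aim 4) | Not by design; families are asked not to disclose |
| Home Care Epic (SAP Appendix) | Not stated; contents and use are not described |

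**Step 2. Reproduce the stated power.** Inputs from the protocol's Aim 4 sample size paragraph: 750 controls, 450 phone, control rate 0.20, decrease 0.071, alpha 0.05, noncompliance 11%. A two-sided test is stated for the secondary outcomes and assumed here for the primary. Noncompliance is treated as dilution in the phone arm:

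- phone rate = 0.20 − 0.89 × 0.071 = 0.1368
- expected difference = 0.0632
- pooled rate = (750 × 0.20 + 450 × 0.1368)/1200 = 0.1763
- null SE = √[0.1763 × 0.8237 × (1/750 + 1/450)] = 0.02272
- alternative SE = √[0.20 × 0.80/750 + 0.1368 × 0.8632/450] = 0.02181
- power = Φ[(0.0632 − 1.96 × 0.02272)/0.02181] = Φ(0.855) = 80.4%

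This matches the stated 80%. Treating noncompliance as an 11% loss of patients in both arms would give 85.5% instead, so dilution is the reading that fits.

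**Step 3. Add receipt in controls.** The documents give no control-arm call rate, so c is an assumption. Control rate = 0.20 − c × 0.071, and the expected difference = 0.071 × (0.89 − c).

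| c (assumed) | Separation in receipt (points) | Expected difference (points) | Power, 750/450 |
|---|---|---|---|
| 0% | 89 | 6.3 | 80.4% |
| 1% | 88 | 6.2 | 79.5% |
| 2% | 87 | 6.2 | 78.7% |
| 5% | 84 | 6.0 | 76.0% |
| 10% | 79 | 5.6 | 71.0% |
| 20% | 69 | 4.9 | 59.8% |

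The difference reaches zero only at c = 89%, the phone arm's own uptake.

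**Step 4. Per-protocol contrast.** Suppose all retained phone-arm children were called, called controls stay in as adherent, and receipt is unrelated to risk. The contrast is then 0.071 × (1 − c): 7.1 points at c = 0, 6.7 at 5% and 6.4 at 10%. The fraction c is the column that the plan would leave blank.

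**Step 5. The SAP's own numbers.** SAP section 1 plans 900 patients randomised 1:1. At 450 per arm the same formula gives 71.7%, 67.1% and 62.1% at c = 0, 5% and 10%. The fall from 80.4% to 71.7% comes from the mismatch with the protocol's 750/450. It exists without any control being called and is a separate matter.

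**The case against.** The strongest reply is that the filter limits one data transfer and not what the hospital records. A call made to a control may well be in Epic or in Home Care Epic, and either could be queried later. The extracted field holds call characteristics, which exist mainly where a call was planned, so the parenthesis may only mark where the field applies. SAP 2.2.4 lets the investigators judge major deviations, and SAP 2.2.8 asks for the reason for any exclusion; neither is limited to one arm. No route to contamination is shown: the call is an addition to standard care, and randomisation follows discharge.

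Most of this stands, and it rules out three stronger readings that a reader might infer:

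- *That a call to a control cannot be detected or is recorded nowhere.* The documents do not support this. They leave control-arm extraction and reporting unplanned; they do not show that records are absent.
- *That a null result could not be told apart from contamination.* Step 3 does not support this. Receipt in 5% to 10% of controls shrinks the expected difference by 0.4 to 0.7 points and would not by itself produce a null.
- *That a control-side noncompliance assumption goes unchecked.* The protocol says only "allowing for 11% noncompliance" and assigns the figure to no arm. Applied wholly to the phone arm, it reproduces the stated power.

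The reply does not close the gap itself. Investigators can exclude a called control only if someone tells them of the call, and no planned step does so. The violation summary is open-ended, but a category with no data feeding it will be empty. That the records may exist supports asking for them.

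**Conclusion.** The point holds as a gap in planned extraction, adherence definition and reporting. Under the SAP as written, a control child who received the nurse call would not be identified by the planned extract and would count as adherent in the per-protocol set. The achieved difference in receipt could not be reported.

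It is not a flaw in the primary analysis. The comparison by allocated group remains valid as an effect of assignment; calls to controls would affect its size and interpretation. Control receipt of 5% to 10% would cost about 4 to 9 points of power at 750/450. These figures rest on an assumed control call rate, on noncompliance acting as dilution in the phone arm only, on the same effect of the call in both arms, and on a two-sided test. If no control was called, the numerical effect is nil and one table row would show it.

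The change is worth making because it is nearly free and makes both the per-protocol set and the separation between arms checkable.

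**What to change.** 1. **SAP Appendix, Data Management Plan.** Replace the parenthesis limiting nurse phone visit data to the intervention arm with *for all randomised patients, both arms*. Run the same nurse phone encounter query for both arms, in CCHMC Epic and, if it holds such calls, in Home Care Epic. State what Home Care Epic contains and how it will be used.
2. **SAP 2.3.1.** Tabulate call receipt within 96 hours of discharge by allocated arm, and show it beside the intention-to-treat result.
3. **SAP 2.2.4.** Reconcile the control-arm adherence rule, and the description of the intervention arm as a home visit arm, with the phone-call intervention.

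An estimate of the effect of receipt, such as the intention-to-treat risk difference divided by the observed difference in receipt, would be an optional added estimand. The SAP does not plan one and this point does not require it.

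The cost is one unfiltered query and one extra table, with no patient contact and no new data system. The query uses existing records, so it was still feasible when the SAP was written (dated 11/3/2016, with enrolment planned to end October 31, 2016). Call fields should travel in a separate file so that follow-up staff stay blinded.
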